7.1.1.1 Eligibility screening

While the investigator is responsible to ensure that each patient meets all inclusion/exclusion criteria prior to randomization, a subset of those criteria have been identified as key eligibility criteria and will also be verified by the sponsor through IRT prior to permitting the patient to be randomization. Patient's eligibility is checked in IRT. The eligibility checklist form must be completed in IRT by the investigator or designee at day 1 prior to starting the treatment phase

and receiving the first dose of study drug (LCI699). Verification of all eligibility criteria must be done prior to contacting IRT. After the eligibility has been checked in IRT and confirmed that the patient is eligible for the trial, then the patient can be enrolled into the treatment phase of the study.

Please refer and comply with detailed guidelines in the IRT manual.

7.1.1.2 Information to be collected on screening failures

Patients who sign an informed consent but fail to be started on treatment for any reason will be considered a screen failure. The reason for not being started on treatment will be entered on the Screening Failure Log, and each patient's demographic information will be recorded on the Demography CRF page.

No other data will be entered into the clinical database for patients who are screen failures, unless the patient experienced a Serious Adverse Event during the Screening Phase (see [Section 8.2](#) for SAE reporting details).

If the patient fails to start the treatment, the IRT must be notified within 2 days of the screen fail that the patient was not enrolled.

7.1.1.3 Patient demographics and other baseline characteristics

The following patient demographics and baseline characteristics will be collected on the CRF:

- Demography including date of birth, sex, predominant race and ethnicity (where permitted),
- Height, weight, waist circumference (see [Section 7.2.2.3](#)),
- Medical history (e.g., important medical, surgical, and allergic conditions from the patient's medical history which could have an impact on the patient's evaluation) / current medical conditions (e.g., all relevant current medical conditions which are present at the time of signing informed consent). Ongoing medical conditions, symptoms and disease which are recorded on the Medical History CRF should include the toxicity grade,
- Information on the most recent prior medical therapy for Cushing's disease will be collected and will include information on drug, dose, duration of therapy and outcomes provided such data are available.
- Where possible, diagnoses and not symptoms will be recorded. Cushing's disease history together with the medication/treatment used will be collected.
- Prior and concomitant medications,

Furthermore the following assessments will be performed:

- Physical Examination (see [Section 7.2.2.1](#)),
- Vital signs including blood pressure and pulse (see [Section 7.2.2.2](#)),
- Patient quality of life questionnaires (CushingQoL, Beck Depression Inventory, HRQoL EQ-5D-5L) (see [Section 7.2.6](#)),
- ECG and 24-hour Holter (see [Section 7.2.2.6](#)),
- MRI, photography and DXA Imaging (see [Section 7.2.2.5](#), [Section 7.2.1.2](#) and [Section 7.2.1.3](#)),

- Laboratory evaluations (e.g., hematology, biochemistry, thyroid panel, coagulation, lipase, glycosylated hemoglobin (HbA1c), fasting insulin and plasma glucose, urinalysis, 24-hour Urinary Free Cortisol and creatinine, testosterone and estradiol, LH and FSH, plasma ACTH, cortisol, 11-deoxycortisol, renin, serum aldosterone, [REDACTED], serum 11-deoxycorticosterone, serum androstenedione, DHEAS, estrone) (see [Section 7.2.2.4](#)),
- Serum pregnancy (see [Section 7.2.2.4.8](#)).

7.1.2 Run-in period

Although there is no Run-in period, washout requirements as described in Inclusion criteria ([Section 5.2](#)) must be followed.

7.1.3 Treatment period

Treatment period is divided in 4 study periods as described in [Section 4.1](#). Patients should be seen for all visits on the designated day with a visit window of ± 3 days and in a fasting state.

During study period 1 (Week 1 to 12), patients will come to the site every 2 weeks. Between visits, they may be contacted by the Investigator/designee in order to increase or decrease the study drug dose based on UFC results from previous visit.

During study period 2 (Week 13 to 24), patients will come to site every 4 weeks. Although study drug dose usually remains stable during this period, adjustment may be needed based on mUFC results and for safety.

Blood samples will be collected for all patients for sparse PK purpose throughout the core study (week 1 – 48). Pharmacokinetic blood collection for a subset of approximately 20 patients will be carried out for extensive PK assessment.

During study period 3 (Week 26 to 34), patients will either continue LCI699 open label if they are not randomized and will have visits every 4 weeks; or will be randomized to one of the 2 arms and will come to site every 2 weeks.

During study period 4 (Week 35 to 48), patients will come to site every 4 weeks.

During study periods 3 and 4, patients are also allowed to have unscheduled visits at any time if they report symptoms of hypercortisolism and have their dose adjusted accordingly.

For details of assessments, please refer to [Table 7-1](#) to [Table 7-5](#) depending on study period.

7.1.4 End of treatment visit including study completion and premature withdrawal

Patients who discontinue study treatment before visit 777 (if patient is in the core phase of the study) or 778 (if patient is in the extension phase of the study), should be scheduled for a visit as soon as possible, at which time all of the assessments listed for the EOT visit will be performed ([Table 7-1](#), [Table 7-3](#) or [Table 7-5](#)) with the following exceptions:

- Patients discontinuing treatment prior to the Week 36 visit do not need to have an EOT core DXA scan

- Patients discontinuing prior to the Week 12 visit or between the Week 24 and Week 36 visits do not need to have an EOT core pituitary MRI (or CT) (i.e. scans are needed if patients discontinue within the 12 week period prior to the Week 24 and Week 48 visits).
- Patients discontinuing or completing extension phase within 36 weeks since their last pituitary MRI (or CT) or DXA scan do not need to have an EOT extension pituitary MRI (or CT) or DXA scans.

An End of Treatment Phase Disposition CRF page should be completed, giving the date and reason for stopping the study treatment. At a minimum, all patients who discontinue study treatment, including those who refuse to return for a final visit, will be contacted for safety evaluations during the 30 days following the last dose of study treatment (Visit 779).

If a patient withdraws or discontinues from the study prematurely, an unscheduled PK sample should be taken, and the sample should be recorded in the “Unscheduled PK” CRF page.

7.1.5 Discontinuation of study treatment

Patients may voluntarily discontinue from the study treatment for any reason at any time. If a patient decides to discontinue from the study treatment, the investigator must make every effort (e.g. telephone, e-mail, letter) to determine the primary reason for this decision and record this information in the patient’s chart and on the appropriate CRF pages. They may be considered withdrawn if they state an intention to withdraw, fail to return for visits, or become lost to follow-up for any other reason.

- The investigator should discontinue study treatment for a given patient if, on balance, he/she believes that continuation would be detrimental to the patient’s well-being.

Study treatment must be discontinued under the following circumstances:

- Emergence of the following adverse events:
 - hypertension defined as office mean sitting systolic BP > 180 mmHg or mean sitting diastolic BP > 110 mmHg (confirmed and persistent*).
- Any of the following laboratory abnormalities (confirmed):
 - hyperkalemia (serum potassium > 6.0 mmol/L).
 - hypokalemia (serum potassium < 2.8 mmol/L).
- Any of the following laboratory abnormalities (confirmed and persistent*):
 - hyperkalemia (serum potassium > 5.5 mmol/L).
 - hypokalemia (serum potassium < 3.0 mmol/L).
 - hyponatremia (serum sodium < 130 mmol/L).
 - AST or ALT >3.0 x ULN combined with total bilirubin >2.0 x ULN without evidence of cholestasis
- QTcF > 500 msec, if confirmed by a cardiologist (see [Section 7.2.2.7](#)).

QTcF > 480 msec, if the investigator determines it is no longer safe for the patient to continue in the study, based on ECGs, cardiac examination, and recommendation from a cardiologist (see [Section 7.2.2.7](#)).

- QTcF increase > 60 msec from pre-first dose baseline measurement.

- Mean increase in QTcF > 30 ms from the mean baseline value at 1.5 hour post-first dose or mean QTcF > 480 ms at day 1 (see [Section 7.2.2.7](#)).
- Pituitary tumor growth, if the tumor is < 2mm from the optic chiasm, or symptoms of actual compression of the optic chiasm emerge (visual field loss, cranial nerve palsies, diplopia) confirmed by MRI of the pituitary.

* Persistent is defined as unresolved with LCI699 dose and/or other concomitant medication changes.

- Pregnancy.
- Use of prohibited concomitant medications (see [Section 6.4.2](#)).
- Any other protocol deviation that results in a significant risk to the patient's safety.

The appropriate personnel from the site and Novartis will assess whether study treatment should be discontinued for any patient whose treatment code has been broken inadvertently for any reason.

Patients who discontinue study treatment should NOT automatically be considered withdrawn from the study. They should return for the assessments indicated in [Section 7.2](#). If they fail to return for these assessments for unknown reasons, every effort (e.g. telephone, email, letter) should be made to contact them as specified in [Section 7.1.8](#).

The investigator must also contact the IRT to register the patient's discontinuation from study treatment.

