¹ The investigator must specify the reduced dose of study drug (LCI699/Placebo) during the randomized withdrawal period, and the reduced dose of LCI699 during the open-label periods of the study. * Abbreviations: UFC, 24-hour urine free cortisol; ULN, upper limit of the normal reference range; LLN, lower limit of the normal reference range.	

In addition, any AE, regardless of suspected drug causality, may require interruption of LCI699 and replacement or stress doses of glucocorticoid therapy until resolution of the event.

- Upon recovery from the AE, the investigator may consider re-starting LCI699 if the dose interruption has been ≤ 14 days.

- If the dose interruption has been > 14 days, then the patient should be observed. If mUFC rises to above the ULN, and has been off glucocorticoid therapy for at least one week, LCI699 may be re-started.

If the patient has interruption of LCI699 for more than 4 weeks, the investigator should consider early discontinuation from the study. Patients that had interruption of LCI699 and mUFC remains \leq ULN off LCI699 should remain on study for observation.

These changes must be recorded on the Dosage Administration Record CRF.

Instructions for monitoring liver function, and the criteria for interrupting, reducing, and re-initiating study drug therapy, or discontinuation of study drug are provided in [Table 6-2](#) below.

Table 6-2 Criteria for interruption and re-initiation of LCI699 for abnormal liver function

Isolated total Bilirubin elevation	
> ULN – 1.5 x ULN > 1.5 - 3.0 x ULN	Maintain dose level Withhold study drug. Monitor liver function tests (LFT) ^a weekly, or more frequently if clinically indicated, until resolved to \leq 1.5 x ULN: If resolved in \leq 14 days, then maintain dose level If resolved in > 14 days, then decrease by one dose level.
> 3.0 - 10.0 x ULN*	Withhold study drug. Monitor LFTs ^a weekly, or more frequently if clinically indicated, until resolved to \leq 1.5 x ULN: If resolved in \leq 14 days, then decrease by one dose level. If resolved in > 14 days, then discontinue patient from study drug treatment. The patient should be monitored weekly (including LFTs ^a), or more frequently if clinically indicated, until total bilirubin has returned to baseline or stabilized over 4 weeks.

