> 10.0 x ULN*	Discontinue patient from study drug treatment The patient should be monitored weekly (including LFTs ^a), or more frequently if clinically indicated, until total bilirubin has returned to baseline or stabilized over 4 weeks.
Isolated AST or ALT elevation	
> ULN - 3.0 x ULN > 3.0 - 5.0 x ULN	Maintain dose level Maintain dose level. Repeat LFTs ^a as soon as possible, preferably within 48-72 hours from awareness of the abnormal results; if abnormal lab values are confirmed upon the repeat test, then monitor LFTs ^a weekly, or more frequently if clinically indicated, until resolved to \leq 3.0 x ULN
> 5.0 - 10.0 x ULN	Withhold study drug. Repeat LFTs ^a as soon as possible, preferably within 48-72 hours from awareness of the abnormal results; monitor LFTs ^a weekly, or more frequently if clinically indicated, until resolved to \leq 3.0 x ULN. Then: If resolved in \leq 14 days, restart study drug and maintain dose level If resolved in > 14 days, restart study drug and decrease dose by one level If not resolved after 4 weeks, discontinue patient from study treatment

> 10.0 x ULN	Discontinue study drug. Repeat LFTs ^a as soon as possible, preferably within 48-72 hours from awareness of the abnormal results; monitor LFTs ^a weekly, or more frequently if clinically indicated, until resolved to ≤ 3 x ULN.
Combined^{b, c} elevations of AST or ALT and total bilirubin	

For patients with normal baseline ALT and AST and total bilirubin value: AST or ALT >3.0 x ULN combined with total bilirubin >2.0 x ULN without evidence of cholestasis^c OR For patients with elevated baseline AST or ALT or total bilirubin value: [AST or ALT >2x baseline AND > 3.0 xULN] OR [AST or ALT > 8.0 xULN], combined with [total bilirubin >2x baseline AND >2.0 xULN]
	
Permanently discontinue patient from study drug treatment.
 
Repeat as soon as possible, preferably within 48 hours from awareness of the abnormal results, then with weekly monitoring of LFTs^a), or more frequently if clinically indicated, until AST, ALT, or bilirubin have returned to baseline or stabilized over 4 weeks.
 
Refer to Section 6.3.3 for additional follow-up evaluations as applicable.

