6.3.3 Follow up on potential drug-induced liver injury (DILI) cases

Patients with transaminase increase combined with Total Bilirubin (TBIL) increase may be indicative of potential DILI, and should be considered as clinically important events.

The threshold for potential DILI may depend on the patient’s baseline AST/ALT and TBIL value; patients meeting any of the following criteria will require further follow-up as outlined below:

- For patients with normal ALT and AST and TBIL value at baseline: AST or ALT > 3.0 x ULN combined with TBIL > 2.0 x ULN
- For patients with elevated AST or ALT or TBIL value at baseline: [AST or ALT > 2 x baseline AND > 3.0 x ULN] OR [AST or ALT > 8.0 x ULN], combined with [TBIL > 2 x baseline AND > 2.0 x ULN]

Medical review needs to ensure that liver test elevations are not caused by cholestasis, defined as ALP elevation $> 2.0 \times \text{ULN}$ with R value < 2 .

Note: (The R value is calculated by dividing the ALT by the ALP, using multiples of the ULN for both values. It denotes whether the relative pattern of ALT and/or ALP elevation is due to cholestatic ($R \leq 2$), hepatocellular ($R \geq 5$), or mixed ($R > 2$ and < 5) liver injury).

In the absence of cholestasis, these patients should be immediately discontinued from study drug treatment, and repeat LFT testing as soon as possible, preferably within 48 hours from the awareness of the abnormal results. The evaluation should include laboratory tests, detailed history, physical assessment and evaluation for the possibility of liver lesions, obstructions/compressions, etc.

- Laboratory tests should include ALT, AST, albumin, creatine kinase, total bilirubin, direct and indirect bilirubin, GGT, prothrombin time (PT)/ international normalized ratio (INR) and alkaline phosphatase.
- A detailed history, including relevant information, such as review of ethanol, concomitant medications, herbal remedies, supplement consumption, history of any pre-existing liver conditions or risk factors, should be collected.
- Further testing for acute hepatitis A, B, C or E infection and liver imaging (e.g. biliary tract) may be warranted.
- Obtain PK sample, as close as possible to last dose of study drug
- Additional testing for other hepatotropic viral infection (CMV, EBV or HSV), autoimmune hepatitis or liver biopsy may be considered as clinically indicated or after consultation with specialist/hepatologist.

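### Protocol safety rules need aligning: eplerenone is permitted in 6.4.1 and Table 6-1 for uses that 6.4.2 prohibits, and the liver and QTcF stop rules in 7.1.5 do not match the sections that implement them

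*Protocol*

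**What the plan says.** **Eplerenone.** Protocol 6.4.1 permits spironolactone and eplerenone to treat or prevent study-drug-related edema or hypokalemia. The hypokalemia row of Table 6-1 suggests either drug for prevention and treatment. Section 6.4.2 puts eplerenone on the prohibited list with two exceptions: acute management after myocardial infarction, and refractory hypokalemia in a patient with hypertension or edema. Section 7.1.5 lists use of a medication prohibited by 6.4.2 among the circumstances in which study treatment must stop.

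**Combined liver elevation.** Section 7.1.5 lists "AST or ALT >3.0 x ULN combined with total bilirubin >2.0 x ULN without evidence of cholestasis" under the heading "Any of the following laboratory abnormalities (confirmed and persistent", and explains: "Persistent is defined as unresolved with LCI699 dose and/or other concomitant medication changes". For the same thresholds in a patient with normal baseline values, Table 6-2 (in 6.3.1) says "Permanently discontinue patient from study drug treatment". Section 6.3.3 says "In the absence of cholestasis, these patients should be immediately discontinued from study drug treatment". For elevated baselines, Table 6-2 and 6.3.3 use relative thresholds ("AST or ALT >2x baseline AND > 3.0 xULN] OR [AST or ALT > 8.0 xULN", with a matching bilirubin condition) that 7.1.5 lacks.

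**QTcF.** Section 7.1.5 makes "QTcF increase > 60 msec from pre-first dose baseline measurement" a mandatory stop, with no condition attached. The body text of 7.2.2.7 reacts to the same rise with triplicate ECGs, interruption if the mean rise is confirmed, and an urgent cardiology consultation. Its outcome branches then turn only on 480 and 500 msec. Three statements there about discontinuation refer the reader to 7.1.7.

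**The concern.** Section 12 allows no authorized deviations, so a site needs one rule for each situation. Where sections differ, what happens to the patient depends on which page the site opens.

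Eplerenone matters most in practice. Protocol 2.7 lists hypokalemia and edema as known risks of LCI699, so a site is likely to look for this advice. A site that follows 6.4.1 or Table 6-1 may find that it has met a mandatory stop criterion in 7.1.5.

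On liver, the section headed as the discontinuation rule carries the weaker condition for a potential drug-induced liver injury signal. On QTcF, a reader of the 7.2.2.7 text alone is not told how the limb above 60 msec ends.

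What is at stake is the handling of patients still on drug in the extension. The Amendment 5 rationale reports 91 ongoing on 25 June 2018. The efficacy results are not at stake.

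**Working it through.** No sample-size, power or alpha figure is involved. The check sets the current operative sections side by side; amendment summaries are not used as evidence of conflict.

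**Eplerenone.** I sorted the uses that 6.4.1 covers against the exceptions in 6.4.2. The sorting is mine; the documents give no such count.

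| Use covered by 6.4.1 | Exception in 6.4.2? |
|---|---|
| Prevent hypokalemia | No |
| Treat non-refractory hypokalemia | No |
| Treat refractory hypokalemia, no hypertension or edema | No |
| Treat refractory hypokalemia with hypertension or edema | Yes |
| Treat edema alone | No |
| Prevent edema | No |

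Six uses less one agreed leaves five in conflict. Table 6-1 supports the three conflicting hypokalemia uses. Its edema row names only spironolactone, so the two edema conflicts lie between 6.4.1 and 6.4.2 alone.

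**Liver, normal baseline.** Take ALT 4.0 x ULN and bilirubin 2.5 x ULN without cholestasis, resolving after interruption. Both values exceed the thresholds (4.0 > 3.0; 2.5 > 2.0).
- Table 6-2 and 6.3.3: off drug immediately and permanently. The repeat test comes after the stop.
- 7.1.5: not a mandatory stop, because the abnormality resolved with a dose change and so was not persistent.

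A site that stops the patient complies with both texts.

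**Liver, elevated baseline.** Take baseline ALT 2.5 x ULN, now 3.5, with bilirubin 2.5 x ULN. Twice baseline is 2 x 2.5 = 5.0, and 3.5 < 5.0, so the combined row of Table 6-2 is not met, while the thresholds in 7.1.5 are. But the row for isolated bilirubin above 1.5 and up to 3.0 x ULN already says "Withhold study drug. Monitor liver function tests (LFT", until the value is 1.5 x ULN or less. Higher bilirubin rows also withhold or discontinue. The one exception is the note for purely indirect bilirubin above 3.0 x ULN, which lets the investigator continue one dose level lower. The thresholds differ, but I claim no dosing conflict here.

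**QTcF, body text of 7.2.2.7 only.** Let b be baseline and Q the on-treatment triplicate mean, in whole msec.
- 7.1.5 stops if Q - b > 60.
- The 7.2.2.7 text asks for nothing more if Q above 480 is not confirmed, lets the patient continue if Q is above 480 without acute cardiovascular risk, and stops if Q > 500.
- The two can differ when b + 60 < Q <= 500, that is, when b < 440. The branch at or below 480 needs b < 420.

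| Baseline | 7.1.5 stops from | Body text: nothing more | Body text: may continue |
|---|---|---|---|
| 410 | 471 | 471-480 | 481-500 |
| 425 | 486 | none | 486-500 |
| 440 | 501 | none | none |

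Exclusion criterion 4 admits baselines up to 450 msec (men) and 460 msec (women), so only the top 10 or 20 msec of the permitted range lies at or above 440. A footnote to Figure 7-2 refers to 7.1.5 and says treatment must stop, but the figure is not shown, so the branch it marks cannot be identified.

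**Pointers.** Section 7.1.7 is the safety follow-up for 30 days after the last dose. It contains no discontinuation criteria. Two of the three pointers speak of a discontinuation procedure and one of criteria.

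**The case against.** The strongest reply is that only eplerenone is a true contradiction.

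On liver, 7.1.5 is a list of mandatory stops. It says nothing about restarting, and it also tells the investigator to stop whenever continuation would harm the patient. Section 6.3.1 names Table 6-2 as the place for interruption, re-initiation and discontinuation rules. A reader might infer that 7.1.5 authorizes a restart after a resolved combined elevation; it does not. This part of the objection stands. What remains is a weaker condition in 7.1.5 that should match Table 6-2.

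On QTcF, a reader might infer that 7.2.2.7 allows dosing to continue after a rise above 60 msec. The text does not say so: its branches are written for 480 and 500 msec, 7.1.5 applies throughout, and the flow chart may state the missing outcome. Section 7.2.2.6.2 adds adverse event entry, a cardiology consult, Medical Monitor notification and central review. This stands too, and limits the point to a gap in the body text.

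On eplerenone, it can be said that Table 6-1 holds only suggestions and that 6.4.2 need not override an explicit permission in 6.4.1. That is fair against any claim that a site following 6.4.1 certainly triggers a stop. It does not remove the conflict, because nothing states which section prevails.

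**Conclusion.** The point holds as a wording conflict that should be fixed, with eplerenone as the main item: five of the six uses that 6.4.1 covers are prohibited by 6.4.2. The liver item is a weaker condition in 7.1.5 for normal baselines, and compliance with Table 6-2 resolves it. The QTcF item is a body-text gap for baselines below 440 msec, conditional on what Figure 7-2 shows. The three misdirected pointers are plain cross-reference errors and do not depend on the figure.

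The liver and QTcF events are probably rare. Protocol 1.2.1.2.4 reports no rise above 60 msec in the healthy-volunteer QT study, and the Amendment 3 rationale reports no known suspected drug-induced liver injury at that time. The 91 patients are those ongoing, not a count of patients who met any of these situations.

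A reader might also infer that the trial's efficacy results or per-protocol sets are compromised. The documents do not support that. RAS and FAS membership does not depend on these rules. SAP Table 2-3 counts codes D01, D02 and M01 only before Week 24 (PPFAS) or the end of randomized withdrawal (PPRAS), so extension dosing cannot alter either set. For the earlier periods, SAP 2.3.4 places the deviation criteria in VAP Module 3, which is not among the documents, so ambiguity in set membership is not shown.

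**What to change.** 1. Give one identical list of permitted eplerenone uses in 6.4.1, Table 6-1 and 6.4.2.
2. In 7.1.5, take the persistence condition off the combined liver bullet and refer to the rule in Table 6-2 and 6.3.3, including its baseline-adjusted thresholds.
3. Use the same wording in 7.1.5 and 7.2.2.7 for the QTcF rise: a triplicate mean increase above 60 msec means discontinuation. Changing only one section would leave a new mismatch, because 7.1.5 now has no confirmation step. In 7.2.2.7, limit the branch that asks for nothing more, and paragraph (c), to rises of 60 msec or less.
4. Redirect the three discontinuation pointers in 7.2.2.7 from 7.1.7 to 7.1.5.

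The cost is wording in five places (7.1.5, 7.2.2.7, 6.4.1, Table 6-1, 6.4.2) plus a site letter. Protocol 12.1 requires a written amendment approved by the sponsor, by Health Authorities where required, and by the ethics boards; the changes can be bundled with the next amendment. No new procedures are needed, past deviations should not be recoded against the new wording, and locked RAS and FAS results do not change.
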